67.5 Gy (RBE) (NTD 81 Gy₁₀, 101 Gy₃) in 15 fractions

For central tumors (within 2 cm of porta hepatis), fractionation will be as follows:

58 Gy (RBE) (NTD 67 Gy₁₀, 79.6 Gy₃)

Underdosing of the PTV will be permitted to maintain normal tissue constraints as described below. However 90% of the PTV should receive the prescription dose. Dose de-escalation will be permitted to maintain a liver EUD below 20 Gy (RBE) and a mean liver dose ≤ 24 Gy (RBE). If dose is de-escalated to below 45 Gy (RBE), the patient will be removed from study and referred as appropriate for further management.

Normal Tissue Constraints:

Spinal cord max dose: 30 Gy (RBE)

Stomach max dose: 42 Gy (RBE)

Bowel (including duodenum, small bowel, large bowel) max dose: 45 Gy (RBE)

CONFIDENTIAL

This document is confidential. Do not disclose or use except as authorized.

Kidney V14 (volume receiving 14 Gy (RBE) < 30%)

Liver-GTV: EUD \leq 20 Gy (RBE), mean dose \leq 24 Gy (RBE)- whichever is lower.

Heart Max dose: 45 Gy (RBE), V40<10%

Chest Wall: no more than 2ccs may receive >60 Gy (RBE)

The deviations in dose constraints described above are considered planning deviations only and will not constitute protocol deviations. Treatment plans that include minor planning deviations may be delivered as part of this protocol. Treatment plans that include major planning deviations may be delivered on this protocol with the review and approval of the PI prior to treatment start. All relevant DVH data regarding doses to critical structures will be maintained in the study database for analysis.

Treatment will be administered on an outpatient basis. Expected toxicities and potential risks as well as dose modifications for are described in Section 6 (Expected Toxicities and Dosing Delays/Dose Modifications). No investigational or commercial agents or therapies other than those described below may be administered with the intent to treat the participant's malignancy.

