5.6 Duration of Follow Up

Study participants will be followed for five years from the completion of study treatment or until death, whichever occurs first. Participants will be removed from follow-up when any of the criteria listed in Section 5.5 apply. Participants removed from treatment or follow-up will be followed for survival outcomes and a 2 years analysis of local control.

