5.7 Criteria for Removal from Study

Participants will be removed from study upon death or withdrawal of consent. The reason for study removal and the date the participant was removed must be documented in the medical record and recorded in the study-specific case report form (CRF). Alternative care options will be discussed with the participant, if applicable.

CONFIDENTIAL

This document is confidential. Do not disclose or use except as authorized.

In the event of unusual or life-threatening complications, participating investigators must immediately notify the Principal Investigator [name] at [REDACTED]

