6.4 Dose Modifications/Delays

Grade 3 or 4 acute toxicity will result in a treatment break until it resolves to Grade 2 or less, with the exception of any Grade 3 Baseline labs that fit the eligibility criteria. Thrombocytopenia will only result in a treatment break if it becomes a Grade 4. All labs will be assessed by the treating physician to determine whether they are considered clinically significant or not clinically significant and treatment will be held at their discretion. If a treatment break of > 14 days is needed, the patient will be removed from study.

7. DRUG FORMULATION AND ADMINISTRATION: Not applicable

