14. STATISTICAL CONSIDERATIONS

The primary objective is to demonstrate proton beam radiation of unresectable primary hepatocellular cancer is associated with local control of at least 80% at 2 years. The null hypothesis is based on a 2-year local control rate of 55% following treatment of tumors >3cm with radiofrequency ablation (RFA), as discussed in 2.3. However, the local control tends to be much poorer in certain subgroups, including tumors unable to be treated by RFA and the largest tumors, thus 55% is used as an upper bound for the sample size considerations.

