14.1 Study Design/Endpoints

The primary endpoint is local control at 2 years, or equivalently, the absence of local failure as defined in 10.3. Starting with a total of 60 patients with unresectable primary hepatocellular cancer, we project 30 of them will be alive at 2 years for the evaluation of local control assuming a 2-year overall survival of 50%. The number of evaluable patients is a conservative assumption based on the historical RFA data and the Tsukuba proton data (13) showing a 2-year overall survival in the range of 50-70%. Analysis of 30 patients alive at 2 years will achieve 94% power to detect a local control rate of 80% if at least 21 of them were free of local failure. The decision rule is associated with 7% probability for accepting the proton protocol is associated with improved local control when the true rate is only 55% at 2 years.

The rate of local control will be based on actuarial estimates, primarily at 2 years, using the Kaplan-Meier method. Time to local failure will be measured from the start of radiation therapy to the date of local failure, as defined in 10.3. Patients who have not failed locally will be censored at the time of last follow-up. A minimum follow-up of 2 years will be required, while patients who die or drop out of the protocol prior to 2 years will be censored at that date.

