14.2 Sample Size/Accrual Rate

The accrual goal was previously revised to 60 patients in order to preserve high power for detecting a slightly smaller but clinically significant increase in local control to 80% at 2 years. Recently, emerging data suggest unresectable liver tumors represent clinically heterogeneous groups, in particular, intrahepatic cholangiocarcinomas are associated with a more favorable prognosis than primary hepatocellular cancers. Thus we propose to restrict the primary hypothesis in 14.1 to the major tumor group, namely patients with unresectable primary hepatocellular cancer. As intrahepatic cholangiocarcinomas constitute one-third of the present enrollment, we propose to continue with their accrual in order to estimate their failure and survival endpoints with reasonable precision for planning future studies for the specific population. Based on the observed distribution of the tumor groups, the target accrual is increased to a total of 90 patients in order to obtain 60 patients with unresectable primary hepatocellular cancer for testing the primary hypothesis in 14.1.

CONFIDENTIAL

This document is confidential. Do not disclose or use except as authorized.

Since the protocol was activated by MD Anderson Cancer Center at the end of September 2010, 47 patients have been enrolled by two participating institutions over a period of 13 months. As of March 2013, their combined accrual has reached 57 patients. We project the increased sample size will be reached within the next year and a half, as the protocol has expanded recently to a third institution. **If a patient is found to be ineligible once registered and therefore taken off study and excluded from analysis, an additional patient may be enrolled and included in analysis.** As specified in 5.6, the patients will be followed for at least 5 years from the completion of protocol treatment or until death, whichever occurs first.

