14.5 Reporting and Exclusions

Not Applicable

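### Section 14.1 does not define drop-out, so patients who start protons and are then removed could be censored within weeks despite the local control follow-up promised in 5.6

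*Combined protocol and SAP*

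**What the plan says.** Five places in the combined protocol and SAP bear on what happens to a patient who comes off protocol treatment.

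- Section 5.1.2.3, on dose: "If dose is de-escalated to below 45 Gy (RBE), the patient will be removed from study".
- Section 6.4, on breaks: "If a treatment break of > 14 days is needed, the patient will be removed from study".
- Section 5.7, whose heading announces the criteria for removal: "Participants will be removed from study upon death or withdrawal of consent". Neither the dose ground nor the break ground appears there.
- Section 5.6: "Participants removed from treatment or follow-up will be followed for survival outcomes and a 2 years analysis of local control". The sentence before it ends follow-up when any criterion in 5.5 applies; those criteria include progression and unacceptable adverse events.
- Section 14.1, on the primary endpoint: local control at 2 years by Kaplan-Meier, timed from the start of radiation, with patients free of local failure censored at last follow-up. It then adds that "patients who die or drop out of the protocol prior to 2 years will be censored at that date".

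On analysis sets, 14.2 allows a patient "found to be ineligible once registered and therefore taken off study and excluded from analysis" to be replaced, while 14.5, the section on reporting and exclusions, reads "Not Applicable".

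**The concern.** The removal rules contradict each other, and the statistical section does not settle the matter. For a patient recorded as removed after a long break, one analyst could apply 14.1 and censor at removal, and another could apply 5.6 and go on counting the patient to 2 years. Each could cite the text. In an open single-arm trial, the primary analysis should not leave that choice until outcomes are known.

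The reasons for removal are not obviously random. Dose is lowered to respect liver limits (5.1.2.3), and breaks follow Grade 3 or 4 toxicity (6.3, 6.4). If those patients fare worse locally, censoring them at removal makes the estimate too favourable.

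**Working it through.** **1. The texts side by side.** Sections 5.1.2.3 and 6.4 each name a ground for leaving the study that 5.7 does not list, so the three cannot all stand. Section 5.6 keeps patients in local control follow-up after they leave treatment. Section 14.1 stops counting drop-outs and does not refer to 5.6, to the dose ground or to the break ground. Whether 14.1 conflicts with 5.6 therefore depends on an undefined term.

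**2. What censoring at removal would do.** A treated patient who is censored still counts in Kaplan-Meier until that date. Treatment takes about 3 weeks (5.5). Removal after a full course's length plus a 14-day break would fall at about 21 + 14 = 35 days, and 35/730 = 4.8% of the 2-year window. Study imaging is only twice yearly (9.1, 9.2), so such a patient would usually be censored before the first follow-up scan. The effect is close to exclusion.

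**3. Patients removed at planning.** The dose rule sits among the planning constraints. A patient removed there may never start radiation and so has no time origin under 14.1. This is a separate gap, which a change to the censoring rule does not close.

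**4. The plan's own figures.** Inputs from 14.1: 60 hepatocellular patients × 50% alive at 2 years = 30 evaluable; success if at least 21 of 30 are free of local failure; rates of 55% and 80%. Exact binomial:

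- P(X ≥ 21 | n = 30, p = 0.55) = 0.0694, against the stated 7%.
- P(X ≥ 21 | n = 30, p = 0.80) = 0.9389, against the stated 94%.

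Both reproduce.

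**5. Illustration on assumed inputs.** The documents give no removal share d and no local control rate q among removed patients. Assume d = 5% to 15% and q = 20% to 40%, add q = 55% as the case where removal is unrelated to outcome, and set the true rate over all patients at 55%. The rate in the remainder is (0.55 − d·q)/(1 − d); for example, (0.55 − 0.10 × 0.20)/0.90 = 0.5889. The last column lets the evaluable number shrink to about 30(1 − d), taken as 28, 27 and 26, with the cut-off still 21.

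| d | q | Rate in remainder | P(X ≥ 21), n = 30 | P(X ≥ 21), n reduced |
|---|---|---|---|---|
| 5% | 40% | 0.5579 | 0.0817 | 0.0293 (n = 28) |
| 5% | 20% | 0.5684 | 0.1006 | 0.0375 (n = 28) |
| 10% | 40% | 0.5667 | 0.0972 | 0.0192 (n = 27) |
| 10% | 20% | 0.5889 | 0.1462 | 0.0328 (n = 27) |
| 15% | 40% | 0.5765 | 0.1170 | 0.0119 (n = 26) |
| 15% | 20% | 0.6118 | 0.2123 | 0.0283 (n = 26) |
| any | 55% | 0.5500 | 0.0694 | 0.0242, 0.0125, 0.0058 |

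With 30 evaluable patients kept, false acceptance is 8% to 21%. With the number reduced and the cut-off fixed, it is 1% to 4%, below the planned 7%, because 21 successes are harder to reach from fewer patients. At any given n it is still higher than in the unrelated-outcome row. When q = 55%, the rate in the remainder stays at 55%. The table applies a binomial rule for patients alive at 2 years, whereas the stated estimator is Kaplan-Meier, so it shows only how far the answer depends on the assumptions.

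**The case against.** The strongest reply is that 14.1 and 5.6 are compatible. Drop-out ordinarily means voluntary withdrawal or loss to follow-up; 14.1 mentions neither the dose nor the break ground; it asks for at least 2 years of follow-up; and 14.2 cites 5.6. On that reading, removed patients stay in the analysis and nothing is lost. This stands as a possible reading, and it is why a reader who infers that these patients are in fact censored as drop-outs goes further than the text. It does not answer the concern, because the other reading is equally open and the word *removed* is used in conflicting ways.

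A second reply is that poor local control in removed patients is only inferred. This also stands. Section 2.3 reports a strong dependence of tumor response on dose, but in photon series and for response, not local control. Nothing in the documents bears on outcome after a long break.

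A third reply is that exclusion of ineligible patients under 14.2 is a different matter, and that a phase II trial may choose to analyse eligible patients. That is fair. The point kept here is only that 14.2 permits exclusions while 14.5 has no plan to report them.

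**Conclusion.** The contradiction between 5.1.2.3, 6.4 and 5.7 is plain from the text. So is the gap in 14.1: an undefined term decides whether follow-up promised in 5.6 enters the primary analysis. On one literal reading, patients who started protons and were then removed are censored within weeks.

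A reader might infer that the local control estimate is therefore optimistic, or that the false-positive rate rises to 8% to 21%. The documents support neither as a finding. That range needs assumed removal shares and outcomes, and an evaluable number that stays at 30; with 26 to 28 evaluable and the same cut-off it is 1% to 4%. The censoring may be informative and may favour the treatment, but its size and direction cannot be established, and no bias arises if removal is unrelated to local control. The design figures in 14.1 are not in dispute. The correction should be made because it is specific, nearly free, and removes a choice that could otherwise be made after outcomes are known.

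**What to change.** - Reconcile 5.1.2.3, 5.6, 5.7, 6.4 and 14.1 so that each removal event has one stated consequence for treatment, follow-up and analysis. No view is taken here on the dose or break limits.
- In 14.1, limit drop-out censoring to withdrawn consent or loss to follow-up. Keep every hepatocellular patient who started protons in the primary analysis, using the follow-up that 5.6 already promises.
- Report separately the number of registered patients removed before starting protons, since they have no time origin under 14.1.
- Replace the entry in 14.5 with a count of, and reasons for, all exclusions, including those that 14.2 allows.

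The cost is protocol and SAP wording and slightly more reporting work. No new follow-up commitment is needed. The local control estimate may come out slightly less favourable.

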14.2 Sample Size/Accrual Rate

The accrual goal was previously revised to 60 patients in order to preserve high power for detecting a slightly smaller but clinically significant increase in local control to 80% at 2 years. Recently, emerging data suggest unresectable liver tumors represent clinically heterogeneous groups, in particular, intrahepatic cholangiocarcinomas are associated with a more favorable prognosis than primary hepatocellular cancers. Thus we propose to restrict the primary hypothesis in 14.1 to the major tumor group, namely patients with unresectable primary hepatocellular cancer. As intrahepatic cholangiocarcinomas constitute one-third of the present enrollment, we propose to continue with their accrual in order to estimate their failure and survival endpoints with reasonable precision for planning future studies for the specific population. Based on the observed distribution of the tumor groups, the target accrual is increased to a total of 90 patients in order to obtain 60 patients with unresectable primary hepatocellular cancer for testing the primary hypothesis in 14.1.

CONFIDENTIAL

This document is confidential. Do not disclose or use except as authorized.

Since the protocol was activated by MD Anderson Cancer Center at the end of September 2010, 47 patients have been enrolled by two participating institutions over a period of 13 months. As of March 2013, their combined accrual has reached 57 patients. We project the increased sample size will be reached within the next year and a half, as the protocol has expanded recently to a third institution. **If a patient is found to be ineligible once registered and therefore taken off study and excluded from analysis, an additional patient may be enrolled and included in analysis.** As specified in 5.6, the patients will be followed for at least 5 years from the completion of protocol treatment or until death, whichever occurs first.

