4.2 Registration Process for DF/HCC and DF/PCC Institutions

The QACT registration staff is accessible on Monday through Friday, from 8:00 AM to 5:00 PM Eastern Standard Time. In emergency situations when a participant must be registered during off-hours or holidays, call the QACT registration line at [REDACTED] and follow the instructions for registering participants after hours.

The registration procedures are as follows:

1. Obtain written informed consent from the participant prior to the performance of any study related procedures or assessments.
2. Complete the protocol-specific eligibility checklist using the eligibility assessment documented in the participant's medical/research record. **To be eligible for registration to the study, the participant must meet each inclusion and exclusion criteria listed on the eligibility checklist.**
3. Fax the eligibility checklist(s) and all pages of the consent form(s) to the QACT at [REDACTED]
[REDACTED]
4. The QACT Registrar will (a) validate eligibility, (b) register the participant on the study, and (c) randomize the participant when applicable.
5. The QACT Registrar will send an email confirmation of the registration and/or randomization to the person initiating the registration immediately following the registration and/or randomization.

CONFIDENTIAL

This document is confidential. Do not disclose or use except as authorized.

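### Section 14.2 drops and replaces registered patients later found ineligible, even after proton treatment and with outcome known, while 14.5 says exclusions do not apply

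*Combined protocol and SAP*

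**What the plan says.** Section 14.2 (Sample Size/Accrual Rate) contains an exclusion and replacement rule: "If a patient is found to be ineligible once registered and therefore taken off study and excluded from analysis, an additional patient may be enrolled". The sentence goes on to say that the replacement counts in the analysis. It sets no time limit, does not separate treated from untreated patients, names nobody to decide, and asks for no blinding to outcome and no sensitivity analysis.

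Section 14.5 (Reporting and Exclusions), where a reader would look for such a rule, says in full: "Not Applicable".

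Other sections bear on it:

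- Section 4.2 puts a central eligibility check before entry: "The QACT Registrar will (a) validate eligibility, (b) register the participant on the study". The 14.2 rule therefore covers errors that surface after that check.
- Section 4.1 requires treatment to start within one month of registration.
- Section 5.6 keeps participants who leave treatment or follow-up under observation for survival and for the 2-year local-control analysis.
- Section 5.7 says: "Participants will be removed from study upon death or withdrawal of consent". Sections 5.1.2.3 and 6.4 name further reasons for removal from study.
- Section 14.1 sets the primary rule for HCC: of 30 patients alive at 2 years, success "if at least 21 of them were free of local failure". It attaches to this a "7% probability for accepting the proton protocol is associated with improved local control when the true rate is only 55% at 2 years".

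**The concern.** The plan has one section that excludes patients from analysis and another that says exclusions do not arise. The rule that does exist is open-ended. Treatment starts within a month of registration, so many late findings of ineligibility would concern patients who have already had protons. Monitoring and source-data verification run through the whole study (12.3), and some criteria in 3.1, such as expected survival above three months or no evidence of extrahepatic tumor, involve judgement that can be revisited.

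Two things are at stake. First, the error rates in 14.1 hold only if exclusion is unrelated to local failure. In an open trial without a control arm, whoever declares a patient ineligible may know the outcome, and no comparator shares the bias. Second, safety and tolerance is a secondary objective (1.3.1). Toxicity in a patient who received protons is informative whether or not that patient met every entry criterion, yet exclusion from analysis takes it out of the 14.4 tables.

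**Working it through.** **Inputs.** From 14.1: n = 30 evaluable patients, success at 21 or more free of local failure, null rate 55%, target rate 80%, and 2-year survival assumed at 50% within a cited range of 50–70%. The number of swapped patients, k, is my assumption; the documents give none.

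**1. The plan's own figures.** With X the number free of local failure among 30:

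- P(X ≥ 21 | p = 0.55) = 0.0694, stated as 7%.
- P(X ≥ 21 | p = 0.80) = 0.9389, stated as 94%.

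Both reproduce.

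**2. Known local failures swapped, rule kept at 21.** Remove up to k local failures and enrol k replacements, each adding a success with probability s. The false-positive rate is

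P(X ≥ 21) + Σ over j = 1…k of P(X = 21 − j) × P(Bin(k, s) ≥ j).

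At p = 0.55: P(X = 20) = 0.0656, P(X = 19) = 0.0976, P(X = 18) = 0.1265.

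*All replacements evaluable at 2 years, s = 0.55:*

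- k = 1: 0.0694 + 0.0656 × 0.55 = 0.1055
- k = 2: 0.0694 + 0.0656 × 0.7975 + 0.0976 × 0.3025 = 0.1513
- k = 3: 0.0694 + 0.0656 × 0.9089 + 0.0976 × 0.5748 + 0.1265 × 0.1664 = 0.2062

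*Replacements with 50% 2-year survival, s = 0.50 × 0.55 = 0.275:*

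- k = 1: 0.0694 + 0.0656 × 0.275 = 0.0875 (0.08746 before rounding, so 8.7%)
- k = 2: 0.0694 + 0.0656 × 0.4744 + 0.0976 × 0.0756 = 0.1079
- k = 3: 0.0694 + 0.0656 × 0.6189 + 0.0976 × 0.1853 + 0.1265 × 0.0208 = 0.1308

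| Failures swapped | 50% survival | 70% survival (s = 0.385) | All evaluable |
|---|---|---|---|
| 0 | 6.9% | 6.9% | 6.9% |
| 1 | 8.7% | 9.5% | 10.6% |
| 2 | 10.8% | 12.5% | 15.1% |
| 3 | 13.1% | 15.9% | 20.6% |

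**3. Exclusion unrelated to local failure.** If patients are excluded without regard to local failure and replaced by patients with the same 55% rate, each of the 30 still has success probability 0.55, and the rate stays at 0.0694.

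**4. Could outcomes be known while replacement was still open?** Section 14.2 describes accrual from the end of September 2010 and projects completion within a year and a half of March 2013, about September 2014. A patient treated before about September 2012 would reach 2 years while a replacement could still be registered.

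**The case against.** The strongest reply is that 14.2 requires an actual finding of ineligibility, and eligibility is set at screening. Later progression does not make a patient ineligible, and an early death does not falsify an expectation of survival. The events most likely to prompt a second look at the baseline scan, new liver lesions or extrahepatic spread, are not local failures under 10.3 to 10.6. Patients with early spread may also die before 2 years and so fall outside the 30. This stands as a limit on size: the figures above assume that every excluded patient is a local failure, and they are bounds, not expectations. It does not supply the missing restriction to baseline data or to untreated patients.

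Several stronger readings are tempting but unsupported:

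- *That the plan allows exclusion at any time, or that patients were swapped.* The open timing is inferred from silence, and nothing shows that an outcome-informed exclusion took place.
- *That 14.2 contradicts an exhaustive list in 5.7.* Section 5.7 does not say that its grounds are the only ones, and 5.1.2.3 and 6.4 give others. These passages need reconciling, but the firm conflict is between 14.2 and 14.5.
- *That toxicity in excluded patients goes unrecorded.* Section 6.1 collects related toxicity of grade 2 or higher from the first dose, section 11 collects adverse events, and the data and safety monitoring committee reviews toxicity quarterly (12.2). The loss is from the final tables.

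It is also fair to say that the entry in 14.5 may be an unfilled template heading, that a primary analysis of eligible patients with an all-treated sensitivity analysis is a defensible alternative, and that the Data and Safety Monitoring Plan is not in the text reviewed and may hold a rule on late ineligibility. None of this removes the conflict between the two sections or returns treated patients to the 14.4 tables.

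**Conclusion.** The point holds as a weakness in the analysis-set rule that should be corrected. Section 14.2 states an exclusion without the limits needed to keep it independent of outcome, and 14.5 denies that there is one. The loss of treated patients from the toxicity tables follows directly from the wording and needs no assumption about motive.

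The effect on the primary test is conditional. For one to three swapped local failures, the false-positive rate moves from 6.9% to between 8.7% and 13.1% at the plan's 50% survival, and to between 10.6% and 20.6% if every replacement is evaluable. This rests on an assumed number of swaps, on all of them being local failures, and on the threshold staying at 21. With exclusion unrelated to local failure there is no inflation. Selective removal of failures would also push the Kaplan-Meier estimate in 14.1 upward; I have not put a figure on that.

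**What to change.** Reword 14.2 so that a patient may be replaced only if found ineligible before the first proton fraction, judged on data that existed before registration. Then write the analysis sets into 14.5:

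- Every patient who receives at least one fraction stays in the toxicity and survival tables.
- Every treated patient with HCC stays in the primary local-control analysis. The limit to HCC matters because the primary hypothesis covers that group alone.
- An eligible-only analysis is reported as a sensitivity analysis.
- Each exclusion is listed with its reason.

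Reconcile this with the follow-up and removal wording in 5.1.2.3, 5.6, 5.7 and 6.4, so that leaving treatment or study is not confused with leaving the analysis. This concerns analysis membership only and does not touch the clinical grounds for removal.

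The cost is protocol wording, with no change to the sample size or the decision rule. A few treated but ineligible patients will slightly dilute the population, and the eligible-only analysis shows by how much. If exclusion cannot depend on outcome, the 14.1 rule keeps its calculated 6.9% false-positive rate and 93.9% power.
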